12.1.5 Unexpected AE (AE or SAE) or SAR

An AE or SAR (whether serious or not) is considered unexpected if the specificity or severity of it is not consistent with the applicable product information (e.g., IB for an unapproved investigational product or package insert/summary of product characteristics for an approved product). Unexpected also refers to AEs or SARs that are mentioned in the IB as occurring with a class of drugs or as anticipated from the pharmacological properties of the drug, but are not specifically mentioned as occurring with the particular drug under investigation.

12.1.6 Other Safety Considerations

Any significant worsening noted during interim or final physical examinations, electrocardiograms, x-rays, and any other potential safety assessments, whether or not these procedures are required by the protocol, should also be recorded as a non-serious or serious AE, as appropriate, and reported accordingly.

12.1.7 Unanticipated Problem (UAP)

An UAP is any incidence, experience or outcome that is unexpected, given the information provided in research-related documentation (e.g., IB, informed consent) and the study population characteristics that is related or possibly related to participation in the research study and places the participant at an increased risk. By this definition, any event that meets the criteria defined in Section 12.1.5 would meet the criteria for a UAP.

However other events may also meet the criteria for a UAP, e.g., a lost or stolen laptop computer that contains sensitive study information.

12.2 Attribution

The relationship to study treatment should be assessed using the following definitions:

Definite	The AE is clearly related to the drug(s) under investigation
Probable	The AE is likely related to the drug(s) under investigation
Possible	The AE possibly related to the drug(s) under investigation
Unlikely	The AE is doubtfully related to the drug(s) under investigation
Unrelated	The AE is clearly not related to the drug(s) under investigation

The investigator is responsible for verifying and providing source documentation for all AEs and assigning the attribution for each event for all subjects enrolled on the trial.

12.3 Timing and Reporting

12.3.1 Adverse Events

All AEs, (including event name, grade, start/stop date and attribution) will be documented. AEs will be collected from the time of D1 of treatment until 90 days after last dose of study treatment. If the subject initiates subsequent anti-cancer therapy prior to 90 days after cessation of study treatment, the reporting period is through 30 days following cessation of study treatment or until the start of the subsequent anti-cancer therapy, whichever is later.

12.3.2 Pregnancy

All initial reports of pregnancy must be reported as an SAE to BMS Worldwide Safety (see Section 12.3.3.2) by the Sponsor-Investigator or designee within 24 hours of becoming aware of the event using the BMS Pregnancy Surveillance Form (provided as a document separate from this protocol). Abnormal pregnancy outcomes (e.g. spontaneous abortion, fetal death, stillbirth, congenital anomaly, ectopic pregnancy) are considered SAEs and must be reported as such.

Any subject who becomes pregnant during the study must be discontinued promptly from all protocol mandated treatment and followed up per protocol.

Follow-up information regarding the course of the pregnancy, including perinatal and neonatal outcome and, where applicable, offspring information must be reported on the Pregnancy Surveillance Form [provided upon request from BMS].

Any pregnancy that occurs in a female partner of a male study participant should be reported to BMS. Information on this pregnancy will be collected on the Pregnancy Surveillance Form.

12.3.3 SAEs

All SAEs, whether related to study treatment or not, including those thought to be associated with protocol-specified procedures, will be collected. SAEs will be reported after informed consent and continuing through 90 days after the discontinuation of all protocol mandated therapy. If the subject initiates subsequent anti-cancer therapy prior to 90 days after cessation of study treatment, the reporting period is through 60 days following cessation of study treatment or until the start of the subsequent anti-cancer therapy, whichever is later. Any SAE occurring after these time periods that is believed to be related to study drug(s) or protocol-specified procedure should also be reported.

It is the responsibility of the Sponsor-Investigator, investigators and the protocol team to ensure SAEs are reported according to the Code of Federal Regulations (CFR), GCP, the protocol guidelines, IRB, and FDA policy.

SAEs will be followed until clinical recovery is complete and laboratory tests have returned to baseline, until progression has been stabilized, or until there has been acceptable resolution of the event. This may at times cause the follow-up period for SAEs to be greater than 90 days. Similarly, the Sponsor-Investigator is responsible for following the subject during the required follow-up period even if the subject lives elsewhere or has been released from his or her care and is being treated under another service at LCI.

12.3.3.1 Reporting to Sponsor-Investigator

All SAEs (whether considered related or not, expected or not) and pregnancies must be reported to the Sponsor-Investigator within 1 business day of awareness.

When new significant information becomes available, a follow-up report must be reported to the Sponsor-Investigator within 1 business day of awareness.

In the event of an unanticipated problem (UAP) as defined in Section 12.1.7 or life-threatening complication the Sponsor-Investigator must be notified via email immediately after awareness.

12.3.3.2 Reporting to BMS Worldwide Safety

All SAEs whether considered related or not, expected or not, and pregnancies must be reported to BMS within 24 hours of Sponsor-Investigator awareness. SAEs are reportable to BMS from informed consent through 60 days after last dose of study treatment. SAEs must be recorded on a BMS approved form; pregnancies must be reported on a Pregnancy Surveillance Form.

SAE Email Address: [contact]
SAE [contact]

If only limited information is initially available, follow-up reports are required. (Note: Follow-up SAE reports should include the same investigator term(s) initially reported.)

If an ongoing SAE changes in its intensity or relationship to study drug or if new information becomes available, a follow-up SAE report should be sent within 24 hours to the BMS (or designee) using the same procedure used for transmitting the initial SAE report.

NOTE: if a report is submitted to the FDA (see Section 12.3.5), a simultaneous copy should be submitted to BMS.

12.3.4 Reporting to the IRB

All events occurring during the conduct of a protocol and meeting the definition of an SAE or UAP will be reported to the IRB per IRB reporting requirements.

12.3.5 Reporting to the FDA

According to CFR 312.32, the Sponsor-Investigator, or designee, will be responsible for notifying the FDA (via Form FDA 3500 (MedWatch Form)) and all participating investigators of any **unexpected fatal or life-threatening events** possibly related with the use of the study drug (drugs) as soon as possible, but in no case later than 7 calendar days after the Sponsor's initial receipt of the information. For all other serious and unexpected safety events, the Sponsor-Investigator, or designee, will notify the FDA within 15 calendar days.

It is the responsibility of the Sponsor-Investigator, investigators, and the Protocol Team to ensure SAEs are reported according to the Code of Federal Regulations, Good Clinical Practices, the protocol guidelines, Institutional Review Board, and FDA policy.

13. DISEASE EVALUATION

13.1 IMWG 2016 Response Criteria

Response	IMWG Criteria*
Abbreviations: NGF=next-generation flow. NGS=next-generation sequencing. FLC=free light chain. M-protein=myeloma protein. SPD=sum of the products of the maximal perpendicular diameters of measured lesions. CRAB features=calcium elevation, renal failure, anemia, lytic bone lesions. FCM=flow cytometry. SUVmax=maximum standardised uptake value. MFC=multiparameter flow cytometry. ¹⁸ F-FDG PET= ¹⁸ F-fluorodeoxyglucose PET. ASCT=autologous stem cell transplantation.	
IMWG MRD Criteria (Requires a complete response as defined below)	

Sustained MRD-negative	MRD negativity in the marrow (NGF or NGS, or both) and by imaging as defined below, confirmed minimum of 1 year apart. Subsequent evaluations can be used to further specify the duration of negativity (e.g., MRD-negative at 5 years)†
Flow MRD-negative	Absence of phenotypically aberrant clonal plasma cells by NGF‡ on bone marrow aspirates using the EuroFlow standard operation procedure for MRD detection in MM (or validated equivalent method) with a minimum sensitivity of 1 in 10 ⁵ nucleated cells or higher
Sequencing MRD-negative	Absence of clonal plasma cells by NGS on bone marrow aspirate in which presence of a clone is defined as less than two identical sequencing reads obtained after DNA sequencing of bone marrow aspirates using the LymphoSIGHT platform (or validated equivalent method) with a minimum sensitivity of 1 in 10 ⁵ nucleated cells § or higher
Imaging-positive MRD-negative	MRD negativity as defined by NGF or NGS plus disappearance of every area of increased tracer uptake found at baseline or a preceding PET/CT or decrease to less mediastinal blood pool SUV or decrease to less than that of surrounding normal tissue ¶
Standard IMWG Response Criteria ; NOTE: see [22, 30 & 31] for additional details	
Stringent Complete Response (sCR)	CR as defined below plus: 
 • normal FLC ratio ** and • absence of clonal cells in bone marrow by immunohistochemistry(κ/λ ratio ≤4:1 or ≥1:2 for κ and λ patients, respectively, after counting ≥100 plasma cells)††
Complete Response (CR)	
 • Negative immunofixation on the serum and urine ‡‡ and • disappearance of any soft tissue plasmacytomas and • < 5% plasma cells in bone marrow aspirates.
Very Good Partial Response (VGPR)	
 • Serum and urine M-protein detectable by immunofixation but not on electrophoresis or • ≥ 90% reduction in serum M-protein plus urine M-protein level < 100 mg/24 h.
Partial Response (PR)	
 • ≥ 50% reduction of serum M-protein plus reduction in 24 hour urinary M-protein by ≥ 90% or to < 200 mg/24 h • If the serum and urine M-protein are unmeasurable, a ≥ 50% decrease in the difference between involved and uninvolved FLC levels is required in place of the M-protein criteria • If serum and urine M-protein are not measurable, and serum free light assay is also not measurable, ≥ 50% reduction in plasma cells is required in place of M-protein, provided baseline bone marrow plasma cell percentage was ≥ 30% • In addition to the above listed criteria, if present at baseline, a ≥ 50% reduction in the size (SPD) §§of soft tissue plasmacytomas is also required
Minimal Response	
 • ≥25% but ≤49% reduction of serum M-protein and • reduction in 24-h urine M-protein by 50–89%. 
In addition to the above listed criteria, if present at baseline, a ≥50% reduction in the size (SPD) §§ of soft tissue plasmacytomas is also required

Stable Disease (SD)	
 • Not meeting criteria for CR, VGPR, PR, minimal response, or PD


Progressive disease (PD)¶¶, 
	
Any one or more of the following criteria:
 
 • Increase of 25% from lowest confirmed response value in one or more of the following criteria: 
 ○ Serum M-protein (absolute increase must be ≥ 0.5 g/dL) ○ Serum M-protein increase ≥ 1 g/dL, if the lowest M component was ≥ 5 g/dL; ○ Urine M-protein (absolute increase must be ≥ 200 mg/24 h); ○ In patients without measurable serum and urine M-protein levels, the difference between involved and uninvolved FLC levels. (absolute increase must be > 10 mg/dL); ○ In patients without measurable serum and urine M-protein levels and without measurable involved FLC levels, bone marrow plasma-cell percentage irrespective of baseline status (absolute increase must be $\geq 10\%$) ○ Appearance of a new lesion(s), $\geq 50\%$ increase from nadir in SPD§§ of >1 lesion, or $\geq 50\%$ increase in the longest diameter of a previous lesion >1 cm in short axis; ○ $\geq 50\%$ increase in circulating plasma cells (minimum of 200 cells per μL) if this is the only measure of disease=

Clinical Relapse
	
Clinical relapse requires one or more of the following criteria:
 
 • Direct indicators of increasing disease and/or end organ dysfunction (CRAB features) related to the underlying clonal plasma-cell proliferative disorder. It is not used in calculation of TTP or PFS but is listed as something that can be reported optionally or for use in clinical practice • Development of new soft tissue plasmacytomas or bone lesions (osteoporotic fractures do not constitute progression) • Definite increase in the size of existing plasmacytomas or bone lesions. A definite increase is defined as a 50% (and ≥ 1 cm) increase as measured serially by the SPD§§ of the measurable lesion • Hypercalcaemia (>11 mg/dL) • Decrease in hemoglobin of ≥ 2 g/dL not related to therapy or other non-myeloma-related conditions • Rise in serum creatinine by 2 mg/dL or more from the start of the therapy and attributable to myeloma; • Hyperviscosity related to serum paraprotein

For MRD assessment, the first bone marrow aspirate should be sent to MRD (not for morphology) and this sample should be taken in one draw with a volume of minimally 2 mL (to obtain sufficient cells), but maximally 4–5 mL to avoid hemodilution.
 
*All response categories require two consecutive assessments made at any time before the institution of any new therapy; for MRD there is no need for two consecutive assessments, but information on MRD after each treatment stage is recommended (e.g. after induction, high-dose therapy/ASCT, consolidation, maintenance). MRD tests should be initiated only at the time of suspected complete response. All categories of response and MRD require no known evidence of progressive or new bone lesions or extra medullary plasmacytomas if radiographic studies were performed. However, radiographic studies are not required to satisfy these response requirements except for the requirement of FDG PET if imaging MRD-negative status is reported.
 
†Sustained MRD negativity when reported should also annotate the method used (e.g. sustained flow MRD-negative, sustained sequencing MRD-negative).
	

‡ Bone marrow MFC should follow NGF guidelines²⁶. The reference NGF method is an eight-colour two-tube approach, which has been extensively validated. The two-tube approach improves reliability, consistency, and sensitivity because of the acquisition of a greater number of cells. The eight-colour technology is widely available globally and the NGF method has already been adopted in many flow laboratories worldwide. The complete eight-colour method is most efficient using a lyophilised mixture of antibodies which reduces errors, time, and costs. 5 million cells should be assessed. The FCM method employed should have a sensitivity of detection of at least 1 in 10⁵ plasma cells.

§ DNA sequencing assay on bone marrow aspirate should use a validated assay such as LymphoSIGHT (Sequentia).

¶ Criteria used by Zamagni and colleagues²⁷ and expert panel (IMPetUs; Italian Myeloma criteria for PET Use)^{28,29}. Baseline positive lesions were identified by presence of focal areas of increased uptake within bones, with or without any underlying lesion identified by CT and present on at least two consecutive slices. Alternatively, an $SUV_{max}=2.5$ within osteolytic CT areas >1 cm in size, or $SUV_{max}=1.5$ within osteolytic CT areas ≤1 cm in size were considered positive. Imaging should be performed once MRD negativity is determined by MFC or NGS.

|| Derived from international uniform response criteria for multiple myeloma.³⁰ Minor response definition and clarifications derived from Rajkumar and colleagues³¹. When the only method to measure disease is by serum FLC levels: complete response can be defined as a normal FLC ratio of 0.26 to 1.65 in addition to the complete response criteria listed previously. Very good partial response in such patients requires a ≥90% decrease in the difference between involved and uninvolved FLC levels. All response categories require two consecutive assessments made at any time before the institution of any new therapy; all categories also require no known evidence of progressive or new bone lesions or extramedullary plasmacytomas if radiographic studies were performed. Radiographic studies are not required to satisfy these response requirements. Bone marrow assessments do not need to be confirmed. Each category, except for stable disease, will be considered unconfirmed until the confirmatory test is performed. The date of the initial test is considered as the date of response for evaluation of time dependent outcomes such as duration of response.

** All recommendations regarding clinical uses relating to serum FLC levels or FLC ratio are based on results obtained with the validated Freelite test (Binding Site, Birmingham, UK).

†† Presence/absence of clonal cells on immunohistochemistry is based upon the $\kappa/\lambda/L$ ratio. An abnormal κ/λ ratio by immunohistochemistry requires a minimum of 100 plasma cells for analysis. An abnormal ratio reflecting presence of an abnormal clone is κ/λ of >4:1 or <1:2.

‡‡ Special attention should be given to the emergence of a different monoclonal protein following treatment, especially in the setting of patients having achieved a conventional complete response, often related to oligoclonal reconstitution of the immune system. These bands typically disappear over time and in some studies have been associated with a better outcome. Also, appearance of monoclonal IgG κ in patients receiving monoclonal antibodies should be differentiated from the therapeutic antibody.

§§ Plasmacytoma measurements should be taken from the CT portion of the PET/CT, or MRI scans, or dedicated CT scans where applicable. For patients with only skin involvement, skin lesions should be measured with a ruler. Measurement of tumor size will be determined by the SPD.

¶¶ Positive immunofixation alone in a patient previously classified as achieving a complete response will not be considered progression. For purposes of calculating time to progression and progression-free survival, patients who have achieved a complete response and are MRD-negative should be evaluated using criteria listed for progressive disease. Criteria for relapse from a complete response or relapse from MRD should be used only when calculating disease-free survival.

||||In the case where a value is felt to be a spurious result per physician discretion (e.g. a possible laboratory error), that value will not be considered when determining the lowest value.

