8.8.3 Bone Marrow Samples

Bone marrow aspirates/biopsies will be collected at the time-points indicated in the Study Calendar in Section 7. In addition to routine clinical evaluation conducted on these samples (including flow cytometry, conventional cytogenetics and fluorescence in situ hybridization [FISH]), samples will also be evaluated for the following correlative studies:

- Flow cytometry-based tumor microenvironment analysis: MRD status will be assessed for this study in part using a flow cytometry-based MM MRD assay developed by the Euroflow consortium utilizing 10 markers (CD138, CD38, CD45, CD19 CD56, CD27, CD117, CD81, κ / λ free light chains) to identify plasma cells, differentiate normal from MM-PC and well as PC clonality. Using alternative gating strategy, this flow cytometry panel will also allow identification and characterization of NK, T, B and myeloid cell subsets.
- MRD assessment by NGS: MRD will be assessed via NGS which utilizes MM cell DNA from bone marrow samples.
- Micro-array / global gene expression analysis of isolated plasma cells.
- Clonal evolution of PC (and MM-PC subpopulation) IgG VJ rearrangement sequencing.

- Immunoseq[®] T cell clonal expansion measurement: DNA will be extracted from CD138- (plasma cell depleted) bone marrow fraction for Immunoseq[®] sequencing of TCR's CRD3 region to be performed on a NGS Illumina[®] platform.

In addition to the volumes required for routine clinical evaluation (if applicable), a minimum of 9mL of bone marrow aspirate (1st pull or 1st technical pull after needle repositioning) will be collected for MRD assessment by flow cytometry and NGS. An additional 10mL of bone marrow aspirate will be collected for CD138+ plasma cell isolation (B cell receptor sequencing).

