14.5.5 Secondary Analysis

The frequencies and proportions of overall response will be calculated. Corresponding 95% confidence intervals will be estimated using the Clopper-Pearson method. OS, PFS, TTP, TTNT, and DoR endpoints will be analyzed using Kaplan Meier techniques. Selected landmarks will be estimated and reported. Logistic regression models and Cox proportional hazards models will be used to analyze the treatment response endpoints as functions of baseline subject and disease characteristics, and results from biomarker studies as previously described. The percent of subjects achieving MRD negative status will be summarized. Subgroup analyses will be conducted for selected efficacy endpoints on the subset of MRD negative subjects (i.e. time to event endpoints).

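### The sequencing MRD-negative row in Section 13.1 has its read threshold reversed, so applied literally it inverts NGS-defined MRD status

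*Combined protocol and SAP*

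**What the plan says.** The Section 13.1 response table has a row for sequencing MRD-negativity. It opens with "Absence of clonal plasma cells by NGS on bone marrow aspirate" and goes on to say that "presence of a clone is defined as less than two identical sequencing reads obtained after DNA sequencing of bone marrow aspirates". It also requires a minimum sensitivity of 1 in 10^5 nucleated cells and permits either a named platform or a validated equivalent. The MRD block of the table applies only to subjects who meet the criteria for complete response.

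Two other rows draw on the sequencing result. Sustained negativity can rest on next-generation flow, on NGS, or on both. The imaging row starts from "MRD negativity as defined by NGF or NGS plus disappearance of every area of increased tracer uptake".

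Section 8.8.3 names both laboratory methods. For flow, "MRD status will be assessed for this study in part using a flow cytometry-based MM MRD assay". For sequencing, "MRD will be assessed via NGS which utilizes MM cell DNA from bone marrow samples". Section 2.4 lists both under the exploratory objectives and plans correlations of immune and T-cell receptor measures with MRD.

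Section 14.5.5, under secondary analysis, says "The percent of subjects achieving MRD negative status will be summarized" and "Subgroup analyses will be conducted for selected efficacy endpoints on the subset of MRD negative subjects", with time-to-event endpoints given as the example. It does not say which method determines MRD status.

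**The concern.** The row contradicts itself. Its first clause makes negativity the absence of a clone; its second says a clone is present when there are few or no identical reads. The limit is written in words, so a lost or garbled symbol does not explain it.

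This sentence is the only NGS calling rule in the protocol. Anyone deriving MRD status from read counts by the written definition would classify a marrow with no matching reads as positive and a plainly clonal one as negative. If NGS supplies the status used in Section 14.5.5, the reported MRD-negative percentage would be wrong and the MRD-negative subgroup would hold the wrong subjects. Associations with NGS-defined MRD under Section 2.4 would point the wrong way.

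**Working it through.** The plan states no figure to reproduce here. The check is a truth table on the written rule, then a look for correcting text elsewhere, then the size of the effect.

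**1. The rule at specific read counts.** Inputs, both from the sequencing row of Section 13.1: a clone is present if identical reads < 2; a subject is MRD-negative if the clone is absent. The last column reverses the inequality (present if reads ≥ 2).

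| Identical reads | Clone, as written | MRD, as written | MRD, inequality reversed |
|---|---|---|---|
| 0 | present | positive | negative |
| 1 | present | positive | negative |
| 2 | absent | negative | positive |
| 3 | absent | negative | positive |
| 50 | absent | negative | positive |

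The two rules disagree at every count. Only the reversed one agrees with the row's opening clause.

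**2. Correcting text elsewhere.** The NGS footnote to the table asks for a validated assay and gives an example, but no read cut-off. Section 8.8.3 gives none. Section 14.5.5 uses MRD status without defining it.

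**3. Effect on a percentage.** Let p be the true NGS-negative share among assessed subjects in complete response. The documents do not give p, so the values below are assumptions. Under the written rule the reported share is 1 − p:

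- p = 10%: 1 − 0.10 = 90%
- p = 25%: 1 − 0.25 = 75%
- p = 40%: 1 − 0.40 = 60%

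At p = 50% the percentage happens to be right, but every subject is still in the wrong group.

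**4. Dependence on the denominator.** The complement holds only when the denominator is assessed subjects in complete response. Suppose 20 such subjects, 5 of them truly negative. Among the 20, 5/20 = 25% becomes 15/20 = 75%. Over all 40 subjects, 5/40 = 12.5% becomes 15/40 = 37.5%, which is not the complement of 12.5% (that would be 87.5%). Section 14.5.5 does not state its denominator.

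**5. Reach.** The flow row has its own definition, with no read count and no reversal. In the sustained and imaging rows, where either method can suffice, a marrow with many identical reads could qualify through NGS even if flow found it positive. VGPR+ (Section 14.3.1) and the 21-of-40 rejection rule (Sections 14.2 and 14.5.4) do not use MRD.

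**The case against.** The strongest reply is that nobody would apply the sentence as written. The row's title and opening clause make the intent plain, and the assay must be validated, so a laboratory would probably report a call from its own rule. Nothing in the documents shows read counts being sent to the study team for classification. This stands: misclassification is a risk of literal application and has not been shown to have occurred. It does not rescue the sentence, because Sections 16.3 and 16.7 require conduct as written and the sentence is the only stated rule.

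A reader might go further and infer that all MRD results in the trial are reversed, that the MRD-negative subgroup is certainly wrong, or that every MRD correlation changes sign. The documents do not support this. Flow is a separate method with a sound definition, and Section 14.5.5 does not say that NGS defines the percentage or the subgroup.

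The reach is also limited. MRD is an exploratory objective and is absent from the secondary objectives in Section 2.2. Section 8.8 and footnote 13 of the Study Calendar say that research samples for correlative analyses are no longer collected as of Amendment 7, Version 8. The correction therefore bears mainly on samples obtained before then, but Section 14.5.5 still plans the MRD analyses.

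Finally, the table is presented as the IMWG 2016 criteria, so the wording may have been carried over from the cited source. That cannot be checked from the documents, and it does not change what the protocol says.

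**Conclusion.** The point holds in a limited form. The read threshold in the sequencing row is inverted relative to the row's own definition, and nothing else in the protocol corrects it. Followed literally, it reverses NGS-defined MRD status for every assessed subject in complete response, and p becomes 1 − p in that group.

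The error carries into the sustained and imaging MRD categories. It carries into the MRD-negative percentage, the subgroup and the MRD correlations only to the extent that they use NGS. The percentages shown rest on assumed values of p and, for the complement, on assessed subjects in complete response as the denominator. The trial's primary conclusion is not at risk. The sentence should still be corrected, because it is an operative classification rule that is wrong as it stands.

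**What to change.** Reword the sequencing row so that a clone counts as absent when fewer than two identical reads are found and, equivalently, as present when there are at least two. Placing a single read on the negative side is inferred from the row's own limit of two, so check the wording against reference 22 before finalising it. Leave the 1 in 10^5 sensitivity requirement unchanged.

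Apply the corrected rule to the NGS samples already collected, and confirm with the laboratory which calling rule produced any results already reported.

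The cost is one phrase in the Section 13.1 table and a check of existing NGS calls. No new samples or procedures are needed.
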